## 11.10 Retention of Data

The investigator shall retain and preserve 1 copy of all data generated during the study, specifically including, but not limited to, those defined by GCP as essential until:

- At least 2 years after the last marketing authorization for the IP has been approved or the sponsor has discontinued its research with the IP, or
- At least 2 years have elapsed since the formal discontinuation of clinical development of the IP.

These documents should be retained for a longer period, however, if required by the applicable regulatory requirement(s) or if needed by the sponsor.

At the end of such period, the investigator shall notify the sponsor in writing of his or her intent to destroy all such material. The sponsor has 30 days to respond to the investigator's notice, and the sponsor has further opportunity to retain such materials at the sponsor's expense.

### 11.11 Financial Disclosure

Trial TNX-OX-CM201 is funded in whole by the sponsor, Tonix Pharmaceuticals, Inc. Sites/institutions must ensure that investigators and all sub-investigators submit a completed financial disclosure form accompanied with a Form FDA 3454 or 3455, as applicable, prior to trial initiation, or as otherwise required in accordance with applicable law.

# 11.12 Publication and Disclosure Policy

No presentations, abstracts (including meeting abstracts), or other publications based on the conduct or results of this study will be permitted without the express written permission of Tonix or its designated agent. All such presentations or publications will proceed only as collaborations between Tonix and the investigators. If the investigator wishes to publish the results of this study, a copy of the proposed manuscript or abstract (including meeting abstracts) will be provided to Tonix or its designee for review, revision, and approval at least 60 days before the expected date of submission for publication, unless otherwise arranged with Tonix in writing. This will enable Tonix to protect its proprietary information and augment the publication with insights or information of which the investigator may not be aware. Patient names and other identifiers, such as photographs or audio or video recordings, may not be disclosed in any publication or public forum without prior written authorization from the patients involved or their legal guardians.

#### APPENDIX A. ICHD-3 DIAGNOSTIC CRITERIA

### 1.1 Migraine without Aura

- A. At least 5 attacks fulfilling criteria B through D
- B. Headache attacks lasting 4 to 72 hours (untreated or unsuccessfully treated)
- C. Headache has at least 2 of the following 4 characteristics:
  - 1. unilateral location
  - 2. pulsating quality
  - 3. moderate or severe pain intensity
- 4. aggravation by or causing avoidance of routine physical activity (e.g., walking or climbing stairs)
- D. During headache at least 1 of the following:
  - 1. nausea and/or vomiting
  - 2. photophobia and phonophobia
- E. Not better accounted for by another ICHD-3 diagnosis

## 1.2 Migraine with Aura

- A. At least 2 attacks fulfilling criteria B and C
- B. One or more of the following fully reversible aura symptoms:
  - 1. visual
  - 2. sensory
  - 3. speech and/or language
  - 4. motor
  - 5. brainstem
  - 6. retinal
- C. At least 3 of the following 6 characteristics:
  - 1. at least one aura symptom spreads gradually over ≥5 minutes
  - 2. two or more aura symptoms occur in succession

- 3. each individual aura symptom lasts 5 to 60 minutes
- 4. at least one aura symptom is unilateral
- 5. at least one aura symptom is positive
- 6. the aura is accompanied, or followed within 60 minutes, by headache
- D. Not better accounted for by another ICHD-3 diagnosis

# 1.3 Chronic Migraine

- A. Headache (migraine-like tension-type-like) on ≥15 days/month for >3 months, and fulfilling criteria B and C
- B. Occurring in a patient who has had at least five attacks fulfilling criteria B-D for 1.1 *Migraine without aura* and/or criteria B and C for 1.2 *Migraine with aura*
- C. On  $\geq 8$  days/month for  $\geq 3$  months, fulfilling any of the following:
  - 1. criteria C and D for 1.1 Migraine without aura
  - 2. criteria B and C for 1.2 Migraine with aura
  - 3. believed by the patient to be migraine at onset and relieved by a triptan or ergot derivative
- D. Not better accounted for by another ICHD-3 diagnosis

## 1. LIST OF ABBREVIATIONS

**Table 1: List of Abbreviations**

Abbreviation	Term
AE	adverse event
AESI	adverse event of special interest
BID	twice daily
BMI	body mass index
CFR	Code of Federal Regulations
CI	confidence interval
CM	chronic migraine
CMH	Cochran-Mantel-Haenszel
CRF	case report form
CSFQ-14	Changes in Sexual Functioning Questionnaire Short-Form
CSR	clinical study report
C-SSRS	Columbia Suicide Severity Rating Scale
ECG	electrocardiogram
EMA	European Medicines Agency
ET	early termination
FDA	Food and Drug Administration
GCP	Good Clinical Practice
HADS	Hospital Anxiety and Depression Scale
ICHD-3	International Classification of Headache Disorders, 3 rd edition
ICH	International Council on Harmonisation of Technical Requirements for Pharmaceuticals for Human Use
IND	Investigational New Drug
IRB	Institutional Review Board
IP	Investigational product
IU	international unit
IWRS	interactive web response system
LOE	lack of efficacy
LS, LSM	least square, least square means
mITT	modified intent-to-treat
MedDRA	Medical Dictionary for Regulatory Activities

Tonix Pharmaceuticals  
Statistical Analysis Plan: TNX-OX-CM201

Abbreviation	Term
MAR	missing at random
MCMC	Markov Chain Monte Carlo
MI	multiple imputation
MIDAS	Migraine Disability Assessment questionnaire
MMRM	Mixed-Effects Model of Repeated Measures
MSI-BPD	McLean Screening Instrument for Borderline Personality Disorder
MSQ	Migraine-Specific Quality of Life Questionnaire
NDA	New Drug Application
NSAIDs	Non-steroidal anti-inflammatory drugs
PGI-C	Patient Global Impression of Change
QAM	Every morning
QPM	Every evening
QD	once daily
SAE	serious adverse event
SAP	statistical analysis plan
SD	standard deviation
SF	screen failure
SOC	system organ class
TEAE	Treatment-Emergent Adverse Event
US	United States
WHO-DD	World Health Organization Drug Dictionary

## 2. PURPOSE OF THE ANALYSES

This statistical analysis plan (SAP) describes the planned analysis and reporting for Protocol TNX-OX-CM201 (A Phase 2, Double-blind, Randomized, Multicenter, Placebo-controlled, Three Arm Parallel Study to Evaluate the Efficacy and Safety of TNX-1900 (Intranasal Oxytocin) in Patients with Chronic Migraine).

The structure and content of this SAP provides sufficient detail to meet the requirements identified by the US Food and Drug Administration (FDA), European Medicines Agency (EMA), and International Council for Harmonisation (ICH) of Technical Requirements for Registration of Pharmaceuticals for Human Use: Guidance on Statistical Principles in Clinical Trials. All work planned and reported for this SAP will follow internationally accepted guidelines for statistical practice, as published by the American Statistical Association and the Royal Statistical Society.

The planned analyses identified in this SAP may be included in clinical study reports (CSRs), regulatory submissions, or future manuscripts. Also, post-hoc exploratory analyses not necessarily identified in this SAP may be performed to further examine study data. Any post-hoc, or unplanned exploratory analysis performed will be clearly identified as such in the final CSR.

- [REDACTED]
- [REDACTED]
- [REDACTED]
- [REDACTED]

The reader of this SAP is encouraged to also read the clinical protocol, and other identified documents, for details on the planned conduct of this study. Operational aspects relating to collection and timing of planned clinical assessments are not repeated in this SAP unless they are relevant to the planned analysis.

### 3. PROTOCOL SUMMARY

This is a double-blind, randomized, placebo-controlled, multicenter, 3 arm Phase 2 study. Men and women with a current diagnosis of chronic migraine (CM) according to the International Classification of Headache Disorders, 3rd edition (ICHD-3) and who meet the criteria for the study at Screening will enter a Run-in Period in which patient's migraine/headache activity will be recorded for at least 28 days. At the end of the Run-in Period, eligible patients will be randomized at a 1:1:1 ratio, to one of the 3 treatment arms: TNX-1900 at a fixed daily dose of 30 IU QAM / placebo QPM (Treatment Arm A), or fixed daily dose of 30 IU QAM / 30 IU QPM (Treatment Arm B), or placebo QAM / placebo QPM (Treatment Arm C), for the duration of a 12-week Treatment Period. Randomization will be stratified by study site and preventive migraine medication (use of a single preventive vs. no preventive). All participants will administer study drug twice a day, mornings and evenings, in a double-blind design.

The study will be conducted in 3 periods (Screening/Washout/Run-in, Treatment, and Safety Follow-up) and will consist of at least 6 visits (Screening Visit, Randomization/Baseline Visit, 3 Treatment Visits, and a Safety Follow-up Visit).

#### Screening/Washout/Run-In (Visit 1: Screening Visit)

After providing written informed consent, patients will be assessed for eligibility (including medical history, migraine headache history, medication use, physical exam, nasal exam, vital signs, clinical labs, and electrocardiogram [ECG]).

Eligible patients will be trained on the e-diary during the Screening Visit and will enter a 28-day Run-In period which will last for at least 28 days. Patients who need to wash out excluded medications will have up to an additional 21 days in the Run-In period, but every effort should be made to minimize to the fewest days needed for the given washout period(s) in the protocol.

During the Run-In, patients will be required to answer questions daily regarding headaches and rescue (abortive) medication use on an electronic diary (e-diary) regardless of whether patients experienced a headache on that day. It is a patient's responsibility to be compliant with e-diary entries. Each patient's headache frequency, as well as e-diary compliance, will be evaluated at the end of the Run-in Period to ensure a patient meets all required eligibility criteria for treatment randomization. A patient must not be informed of the minimum number of headache days and migraine headache days required to be randomized to study treatment as this might bias e-diary entries during Run-in Period.

During this Screening and Run-In Period, if any test results come back and indicate a patient's ineligibility for the study, the patient should be considered a screen-failure (SF) and informed that they are not eligible for the study and can stop completing the e-diary. However, if the investigator determines that the patient should be brought back into the clinic for re-testing, the patient should continue completing the e-diary until a final determination regarding eligibility is made.

In addition, any patients not meeting the randomization criteria will be considered a failure.

**Double-blind Treatment Period (Visit 2: Randomization/Baseline; Visits 3, 4, 5: Treatment)**

The Treatment Period will last for about 84 days. At Visit 2, eligible patients will be randomized in a 1:1:1 ratio to one of 3 treatment arms (A, B or C) as summarized above. Randomization will be stratified by study site and concomitant migraine preventive medication (up to one is allowed). Patients will be required to answer daily headache questions and study drug compliance on an e-diary during the Treatment Period regardless of whether a headache was experienced that day.

[figure not shown]
All patients who withdraw early from the study will be encouraged to complete an Early Termination Visit for safety evaluations (Visit 5 [V5]) within 7 days of withdrawal from the study. Study end is after Visit 5/ET. A Safety Follow-up Visit (Visit 6 [V6]) will occur 14 days after V5/ET.

**Safety Follow-up Period (Visit 6)**

Approximately 14 days (+4 days) after Visit 5 or End of Treatment (ET), all randomized patients will attend a Safety Follow-up Visit.

A schema of the study design is provided in [Figure 1](#).

**Figure 1: Study Schema**

## **4. ANALYSIS SAMPLES**

The following populations will be utilized for the analyses of data. Disposition of patients will use the All Patients Population. The safety analyses will be conducted on the Safety Population. The modified intent-to-treat (mITT) Population will be used for the primary efficacy analyses.

### **4.1. All Patients Population**

This includes all patients available in the electronic data capture system; patients will be presented by their randomized treatments (if applicable).

### **4.2. Modified Intent-to-Treat Population**

The mITT population will include all randomized patients who received at least one dose of study drug and had at least one post-Baseline evaluable month (that is, at least one of the three 28-day periods has at least 14 non-missing e-diary entries; see Section 9.1.1). This population will be used to summarize the primary and other efficacy data. Patients will be analyzed according to randomized treatment assignment.

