### 5.2. Key Secondary Efficacy

There are six key secondary efficacy endpoints. For all, the target population is all patients in the mITT population with CMs as defined by the inclusion/exclusion criteria. The key secondaries (in order) are:

- Proportion of patients experiencing a  $\geq 50\%$  reduction in the number of migraine headache days from the last 28 days of Baseline to the month 3 28-day normalized migraine headache days. The percent change from baseline will be calculated for each month as  $100 * [\text{monthly count} - \text{baseline count}] / [\text{baseline count}]$ .
  - A composite strategy will be employed to handle missing data and discontinuation. Concomitant medications and all other intercurrent events will use a treatment policy strategy; data will be analyzed as observed. For all missing data (whether or not due to discontinuation), they will be assumed to be non-responders; that is, failure to stay on-trial and provide data is assumed to reflect non-response to study treatment.
  - The population-level summary will be the percentages of responders in each arm and difference in percentages of responders between treatment arms (analyzed as randomized) at month 3. See Section 9.1.4.2 for full details

- Mean change in the number of days using rescue medication (triptan, ergot derivative, or other migraine-specific acute medication) from the last 28 days of Baseline to the last 28 days of treatment.
  - A “while on treatment” policy strategy will be used for all intercurrent events. That is, the data will be considered independently from any intercurrent event, such as study discontinuation. The approach for partial and missing data is described in Section 9.1.1 (Missing data approach will be identical to that of the primary endpoint).
  - The population-level summary will be the model-based least-squared means for each arm and differences between treatment arms (analyzed as randomized) at month 3. See Section 9.2.1.1 for details.
- Proportion of patients with a Patient Global Impression of Change (PGIC) rating of 1, “very much improved”, or 2, “much improved”, at Week 12.

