  - A composite strategy will be employed to handle missing data and discontinuation. Concomitant medications and all other intercurrent events will use a treatment policy strategy; data will be analyzed as observed. For all missing data (whether or not due to discontinuation), they will be assumed to be non-responders; that is, failure to stay on-trial and provide data is assumed to reflect non-response to study treatment.
  - The population-level summary will be the percentages of responders in each arm and difference in percentages of responders between treatment arms (analyzed as randomized) at month 3. See Section 9.2.1.2 for full details
- Mean change in the number of moderate or severe headache days from the last 28 days of Baseline to the last 28 days of treatment. A moderate or severe headache day is defined as any calendar day wherein a patient records a headache or migraine of moderate or severe peak intensity in the e-diary.
  - A “while on treatment” policy strategy will be used for all intercurrent events. That is, the data will be considered independently from any intercurrent event, such as study discontinuation. The approach for partial and missing data is described in Section 9.1.1 (Missing data approach will be identical to that of the primary endpoint).
  - The population-level summary will be the model-based least-squared means for each arm and differences between treatment arms (analyzed as randomized) at month 3. See Section 9.2.1.3 for details.
- Mean change in the number of migraine headache days from the last 28 days of Baseline to average number per 28 days over the entire 12 week duration of Treatment Period.
  - A “while on treatment” policy strategy will be used for all intercurrent events. That is, the data will be considered independently from any intercurrent event, such as study discontinuation. The approach for partial and missing data is

described in Section 9.1.1 (Missing data approach will be identical to that of the primary endpoint).

- The population-level summary will be the model-based least-squared means for each arm and differences between treatment arms (analyzed as randomized) at month 3. See Section 9.1.4.1 for details.
- Mean change from Baseline in the Migraine-Specific Quality of Life Questionnaire Role Function, Restrictive domain (MSQ v2.1) at Week 12.

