##### **9.1.4.2. Patients Experiencing a $\geq 50\%$ Reduction in Migraine Headaches**

Finally, for each patient and month, patients will be flagged as responders if they experience a  $\geq 50\%$  reduction in the number of migraine headache days from the last 28 days of Baseline to the given month's 28-day normalized migraine headache days. The percent change from baseline will be calculated for each month as  $100 * [\text{monthly count} - \text{baseline count}] / [\text{baseline count}]$ . The number and percentage of patients achieving  $\geq 50\%$  improvement will be reported as well as 95% CIs for the percentages. Patients with missing data will be considered non-responders/ not achieving either improvement threshold. The difference in percentages in the active and placebo arms from the Cochran-Mantel-Haenszel (CMH) common risk difference estimator will be reported along with its 95% CI based on the Sato variance estimator. Pairwise p-values will compare each treatment arm to placebo based on a CMH stratified by preventive medication use. The primary time point of interest will be month 3, but each month will be summarized.

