## 9.2. Secondary Endpoints

All secondary efficacy analyses will be based on the mITT population.

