#### 9.2.1.2. Patient Global Impression of Change

The number and percentage and 95% CIs for the percentages will be reported for patients with a PGIC rating of 1, “very much improved”, or 2, “much improved”, at Week 12 for each treatment group. Patients with missing data will be considered non-responders. The difference in percentages in the active and placebo arms will be reported along with its 95% CI (using the Sato estimator of variance). Pairwise p-values will compare each treatment arm to placebo based on a

CMH stratified by preventive medication use. The primary time point of interest will be Week 12, but each time point collected will be summarized.

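### The binary endpoints score missing data as non-response, but the mITT rule drops the earliest leavers from the denominator

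*SAP*

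**What the plan says.** **Population.** SAP 4.2 requires randomisation, at least one dose, and that the patient "had at least one post-Baseline evaluable month (that is, at least one of the three 28-day periods has at least 14 non-missing e-diary entries". It adds: "This population will be used to summarize the primary and other efficacy data". Protocol 10.3.2 and the synopsis give the same rule. SAP 5.2 says of the six key secondaries: "For all, the target population is all patients in the mITT population with CMs as defined by the inclusion/exclusion criteria". SAP 9.2 says: "All secondary efficacy analyses will be based on the mITT population".

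**Missing outcomes.** For the ≥50% responder and PGIC responder endpoints, SAP 5.2 uses a composite strategy: "For all missing data (whether or not due to discontinuation), they will be assumed to be non-responders". Its stated reason is that "failure to stay on-trial and provide data is assumed to reflect non-response to study treatment". The analysis sections repeat the rule: SAP 9.1.4.2 ("Patients with missing data will be considered non-responders/ not achieving either improvement threshold"), SAP 9.2.1.2 ("Patients with missing data will be considered non-responders") and SAP 9.2.3 for the ≥75% responder endpoint and the proportion below 14 headache or 8 migraine days. Protocol 10.1.3 agrees.

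**Testing.** Under SAP 8.1.5 the ≥50% responder endpoint is the first key secondary. It is reached only after both doses succeed on the primary. The stronger dose is tested at 0.025 and, if it passes, the other at 0.05. A failure stops all later tests.

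**The concern.** Entry to mITT depends on what a patient does after dosing. The composite strategy treats leaving and giving no data as failure, yet the patients who do this soonest are removed instead of counted. The diary condition suits the primary MMRM, which needs at least one evaluable month. A composite binary endpoint does not need it, because every dosed patient has a defined outcome.

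If very early exit differs between arms, the responder difference shifts in favour of the arm that loses more patients early. Two of the affected endpoints are alpha-controlled, and a changed decision on the first carries down the hierarchy. For PGIC, a diary rule also sets the denominator of an endpoint measured at visits.

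**Working it through.** **Who is excluded.** The condition applies within each period, so the total number of entries does not decide membership:

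| Diary entries, Months 1 / 2 / 3 | Total | In mITT? | ≥50% responder status at Month 3 |
|---|---|---|---|
| 14 / 0 / 0 | 14 | yes | missing, so non-responder |
| 13 / 0 / 0 | 13 | no | not counted |
| 13 / 13 / 13 | 39 of 84 | no | not counted |

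Every dosed patient outside mITT has at most 13 entries in Month 3. That month is therefore not evaluable, and the SAP's own rule would score each of them a non-responder on the migraine-day responder endpoints. For PGIC, SAP 8.1.3 maps a very early termination visit to Week 4, which leaves Week 12 missing and again a non-response. A patient with a sparse diary but a recorded Week 12 PGIC would lose a real observation.

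**How many.** The documents give no figure for mITT exclusions. The study schema (Protocol 3.1, Figure 1) expects 265 completers of 300, so 35 non-completers, or 35/3 = 11.7 per arm. Exit timing is not stated. Assuming exits spread evenly over 84 days:

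- 14 entries in 14 days: 11.67 × 14/84 = 1.94 per arm.
- 14 entries at 82% completion (the run-in minimum): 14/0.82 = 17.1 days; 11.67 × 17.1/84 = 2.37 per arm.

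With equal underlying exit, a gap of 3 or more between two arms, in either direction, has probability 0.194 (mean 1.94) to 0.240 (mean 2.37), from the difference of two Poisson counts.

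**Shift in the estimate.** Assume 100 dosed and 35 responders per arm, so the true difference is 0. The mITT rate is 35/(100 − excluded).

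| Excluded, active v placebo | Rates | Difference |
|---|---|---|
| 2 v 2 | 35.7% v 35.7% | 0 |
| 4 v 1 | 36.5% v 35.4% | +1.1 points |
| 1 v 4 | 35.4% v 36.5% | −1.1 points |

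The standard error is √(2 × 0.35 × 0.65/100) = 6.75 points, so 1.1 points is 0.16 SE.

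**Borderline cases.** These use assumed counts and a pooled two-proportion z-test, two-sided, unstratified as a stand-in for the planned CMH test. The threshold is 0.025.

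| All dosed | p | Excluded | mITT | p |
|---|---|---|---|---|
| 39/100 v 25/100 | 0.0338 | 2 v 2 | 39/98 v 25/98 | 0.0330 |
| 39/100 v 25/100 | 0.0338 | 4 v 1 | 39/96 v 25/99 | 0.0223 |
| 40/100 v 25/100 | 0.0235 | 1 v 4 | 40/99 v 25/96 | 0.0334 |

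**Error rate.** This was simulated with 100 dosed per arm, 30% responders in both arms among all dosed, and excluded patients as non-responders. With equal exit of 1.94 or 2.37 per arm, the two-sided error at 0.025 stays at about 2.5% on either denominator. With assumed early exit of 5% active v 1% placebo, the one-sided false-positive rate in favour of active rises from 0.0125 to about 0.020; with 8% v 2%, to about 0.026.

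**The case against.** The strongest reply is that the plan is consistent and prespecified. Both documents name mITT, and SAP 5.2 states the target population before applying the composite strategy within it. Population and intercurrent-event strategy are separate estimand attributes. That stands: this is a poor fit with the stated rationale, not a contradiction. It does not remove the dependence of the denominator on behaviour after dosing.

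Second, chance gaps do no systematic harm. With equal underlying exit the test keeps its level. Even at true rates of 39% v 25%, the conclusion in favour of active changes in only 3.0% to 3.4% of simulated trials, in both directions. This also stands. Bias needs early exit that differs by treatment, and the documents give no basis for estimating that.

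Third, the borderline counts were chosen to sit near 0.025, and the second dose is tested at 0.05, where 0.034 and 0.022 lead to the same decision. This is fair: the examples show what can happen, not what is likely. The 13/13/13 diary is also improbable, given the 23-of-28-day run-in requirement and site contact after two missed days.

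Fourth, SAP 6.1 reports population counts and reasons for discontinuation, and SAP 7.3 summarises diary compliance. These would show much of any imbalance, but not why each patient is outside mITT, and they give no corrected estimate. A wider analysis may sit in redacted text (SAP 8.1.1 and 13) or in SAP 9.1.3.3, which appears cut short; none is visible.

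**Conclusion.** The concern holds as a low-cost improvement. On four binary endpoints, two of them alpha-controlled, mITT removes the earliest leavers, whom the SAP's own reasoning would count as non-responders. No visible planned analysis restores them. The effect is probably small: about 2 patients per arm if exits are evenly spread, almost no effect if exclusions are equal, and about 1 percentage point for a 4 v 1 split, in either direction. It could change a decision only near the threshold. The primary MMRM is unaffected. These sizes rest on assumed exit timing, assumed responder rates and an unstratified test.

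**What to change.** Add a set to SAP Section 4: *all randomised patients who took at least one dose, analysed as randomised*. The Safety Population has the same members but is analysed by treatment received, so it cannot stand in. Use the new set for the ≥50% responder, PGIC responder, ≥75% responder and below-14-headache/below-8-migraine-day endpoints. Score missing outcomes as non-response, and use the recorded Week 12 PGIC where there is one.

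State the exceptions in SAP 4.2, 5.2, 9.1.4.2, 9.2, 9.2.1.2 and 9.2.3, and record in SAP 13 the departure from Protocol 10.3.2 and the synopsis. Keep the primary MMRM and its sensitivity analyses on mITT. In SAP 6.1, add the reason for each mITT exclusion, by arm.

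If the sponsor keeps mITT for these endpoints, prespecify the all-dosed, as-randomised responder analysis as a sensitivity analysis before unblinding.

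The cost is one definition, six section edits, one entry in SAP 13, one addition to the disposition summary and one population flag, with no new data. The fallback costs one extra analysis, besides the added exclusion reasons. The downsides are slightly lower responder percentages, denominators that differ from the primary's, and a documented departure from the protocol's efficacy population.
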